9.3 Procedures at each visit

The following visits will be conducted: screening, T0, T1, T2, T3 and T4.

9.3.1 Screening

The screening will be performed on the day patients are admitted to the participating wards. All patients admitted to these respective wards will be screened. The screening will consist in a brief clinical interview and filling in the Insomnia Severity Index. In the clinical interview, patients will briefly be asked about their sleep problems and their medical history by a trained physician. The aim is to determine whether the diagnostic criteria for acute insomnia are fulfilled and whether any exclusion criteria are fulfilled. Patients need a total score > 7 on the Insomnia Severity Index to be included. For details regarding this questionnaire, please see chapter 5.

9.3.2 Timepoints T0 to T4

Time point T0 (day 0):

- Insomnia Severity Index
- Brief Symptom Inventory
- Beck Depression Inventory
- Visual analogue scales (subjective sleep quality, mood, concentration, and tiredness)
- Sleep diary will be handed out
- medication status
- adverse events

Time point T1 (day 7±2):

- Insomnia Severity Index
- Visual analogue scales (subjective sleep quality, mood, concentration, and tiredness)
- sleep diary will be checked
- medication status
- adverse events

Time point T2 (day 14±2):

- Insomnia Severity Index
- Brief Symptom Inventory
- Beck Depression Inventory
- Visual analogue scales (subjective sleep quality, mood, concentration, and tiredness)
- sleep diary will be checked
- medication status
- adverse events

Time point T3 (day 84±7):

- Insomnia Severity Index
- Visual analogue scales (subjective sleep quality, mood, concentration, and tiredness)

- sleep diary will be checked
- medication status
- adverse events

Time point T4 (day 182±7):

- Insomnia Severity Index
- Brief Symptom Inventory
- Beck Depression Inventory
- Visual analogue scales (subjective sleep quality, mood, concentration, and tiredness)
- sleep diary will be checked
- medication status
- adverse events

For details regarding the mentioned questionnaires, please see chapter 5.

10. SAFETY

10.1 Drug studies

Not applicable

10.2 Medical Device Category C studies

Not applicable

10.3 Medical Device Category A studies

Device deficiencies and all **adverse events (AE)** including all **serious adverse events (SAE)** are collected, fully investigated, and documented in the source document and appropriate case report form (CRF) during the entire study period, i.e. from patient's informed consent until the last protocol-specific procedure. Documentation includes dates of event, treatment, resolution, assessment of seriousness, and causal relationship to device and/or study procedure [ISO 14155, 6.4.1.].

10.3.1 Foreseeable adverse events and anticipated adverse device effects

Potential adverse events are transitional worsening of the sleep disorder and / or the mental disorder, daytime tiredness and daytime sleepiness. No SAE that could be related to the investigational device or study procedures are expected during this clinical trial.

10.3.2 Definition and Assessment of safety related events

Adverse Event (AE):

Any untoward medical occurrence, unintended disease or injury or any untoward clinical signs (including an abnormal laboratory finding) in participants, users or other persons whether or not related to the investigational medical device [ISO 14155: 3.2].

This includes events related to the investigational device or the comparator and to the procedures involved. For users or other persons this is restricted to events related to the investigational medical device.

Adverse Device Effect (ADE):

Adverse event related to the use of an investigational medical device [ISO 14155: 3.1].

This includes any adverse event resulting from insufficient or inadequate instructions for use, deployment, implantation, installation, operation, or any malfunction of the investigational medical device. This includes any event that is a result of a use error or intentional misuse.

Serious Adverse Event (SAE) [European regulation on medical devices 2017/745, art. 58]:

Any adverse event that led to any of the following:

- (a) death,
- (b) serious deterioration in the health of the subject that resulted in any of the following:
 - (i) life-threatening illness or injury,
 - (ii) permanent impairment of a body structure or a body function,
 - (iii) hospitalisation or prolongation of patient hospitalisation,
 - (iv) medical or surgical intervention to prevent life-threatening illness or injury or permanent impairment to a body structure or a body function,
 - (v) chronic disease,
- (c) foetal distress, foetal death or a congenital physical or mental impairment or birth defect.

These are submitted to the EC via BASEC within 7 days (see below chapter 10.2.3). A planned hospitalisation for pre-existing condition, or a procedure required by the protocol, without a serious deterioration in health, is not considered to be a serious adverse event.

Device deficiency:

Inadequacy of a medical device related to its identity, quality, durability, reliability, safety or performance,

such as malfunction, misuse or use error and inadequate labelling [ISO 14155: 3.15].

Device deficiency with SAE potential:

Device deficiencies that might have led to a serious adverse event if a) suitable action had not been taken or b) intervention had not been made or c) if circumstances had been less fortunate.

Health hazards that require measures:

Findings in the trial that may affect the safety of study participants and, which require preventive or corrective measures intended to protect the health and safety of study participants SAE [ClinO Art. 37].

Causal Relationship of SAE [MEDDEV 2.7/3 revision 3, May 2015]:

A causal relationship towards the medical device or study procedure should be rated as follows:

- **Not related:** The relationship to the device or procedures can be excluded.
- **Unlikely:** The relationship with the use of the device seems not relevant and/or the event can be reasonably explained by another cause, but additional information may be obtained.
- **Possible:** The relationship with the use of the investigational device is weak but cannot be ruled out completely. Alternative causes are also possible.
- **Probable:** The relationship with the use of the investigational device seems relevant and/or the event cannot reasonably be explained by another cause.
- **Causal relationship:** The serious event is associated with the investigational device or with procedures beyond reasonable doubt.

Device deficiencies that might have led to an SAE are always related to the medical device.

10.3.3 Reporting of Safety related events

Reporting to Sponsor-Investigator:

All SAEs, device deficiencies and health hazards that require measures are reported to the Sponsor-Investigator within 24 hours upon becoming aware of the event. Device deficiencies are assessed regarding their potential to lead to an SAE.

Pregnancies

Reporting of pregnancy is not necessary in this study.

Reporting to Authorities:

The sponsor-investigator will apply to the notification requirements specified in Art. 15 of the MedDO of 17 October 2011 (SR 812.213).

The sponsor investigator will report to the Ethics Committee via BASEC **device deficiencies** that could have led to serious adverse events if suitable action had not been taken, intervention had not been made, or circumstances had been less fortunate within 7 days [ClinO Art. 42].

Health hazards that require measures are reported to the Ethics Committee via BASEC within 2 days [ClinO Art. 37].

Periodic safety reporting:

A yearly safety update-report is submitted by the Investigator to the Ethics Committee via BASEC.

A report is submitted to Swissmedic by the Sponsor-Investigator, as defined in Art. 15a,b of the MedDO of 17 October 2011 (SR 812.213).

10.4 Assessment, notification and reporting on the use of radiation sources

Not applicable.

11. STATISTICAL METHODS

11.1 Hypothesis

Hypothesis: SleepExpert improves insomnia and general mental health in patients with severe mental disorders.

Primary objective: To assess whether there is a significantly greater reduction in self-assessed insomnia severity (as measured by the Insomnia Severity Index, ISI) across six months (interaction Group x Time) in patients in the Tau plus SleepExpert group, compared to patients in the TAU plus sleep monitoring group.

Secondary objective: To assess whether there is a significantly greater improvement in general mental health (Brief Symptom Inventory) across six months (interaction Group x Time) in patients in the TAU plus SleepExpert group, compared to patients in the TAU plus sleep monitoring group.

Exploratory objectives: Additional objectives include the effect of TAU plus SleepExpert versus TAU plus SleepMonitoring on the following parameters:

- severity of depressive symptoms (Beck Depression Inventory, BDI)
- mood, tiredness, concentration, and subjective sleep quality (self-constructed visual analogue scales)
- daytime sleepiness (Epworth Sleepiness Scale)
- medication
- hospitalization

11.2 Determination of Sample Size

A power analysis was conducted with G-Power (Faul, Erdfelder, Lang, & Buchner, 2007). Assuming an alpha error level of 0.05 (two-sided) and a power of 0.8, a total sample size of n=60 will be sufficient to detect a medium effect (Cohen's d=0.65). This is a pilot trial with the primary aim of collecting qualitative experience and preliminary efficacy data. A large confirmatory trial will be conducted if the results of this pilot trial are encouraging.

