6. STUDY DESIGN

6.1 General study design and justification of design

This project is a prospective randomized controlled clinical pilot trial with a cluster-crossover design

involving two groups: An interventional group (TAU, plus SleepExpert) and a control group (TAU plus sleep monitoring).

Two different wards in the trial site (UPD Bern) will constitute the clusters. The study is conceptualized with a crossover, i.e. clusters (wards) will first be randomized to one of the groups for a duration of 4 months. After a washout-phase of two months, they will then be allocated to the other group for another 4 months. The order (TAU plus SleepExpert first vs. TAU plus sleep monitoring first) will be randomly allocated in a 1:1 fashion.

A total of 60 patients will be included. Patients will be assessed before the intervention (T0) and at the following time-points after the start of the intervention: 1 week (T1), 2 weeks (T2), 12 weeks (T3) and 26 weeks (T4).

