9.2.5 Assessments in participants who prematurely stop the study

For participants who discontinue the study intervention but do not withdraw from participation in the study, study visits and data collection will continue in the same way as for non-withdrawn participants.

Dropouts before start of treatment (i.e. non-starters) will be replaced by recruitment of new participants.

Patients who started the intervention but who were prematurely withdrawn from the study will not be replaced by newly enrolled patients.

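### On its stated inputs (d=0.65, two-sided 5%), a total of 60 patients gives about 70% power, not 80%; 60 is what a one-sided test would need.

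*Combined protocol and SAP*

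**What the plan says.** Section 11.2 (Determination of Sample Size) reports that "A power analysis was conducted with G-Power" and gives the result as: "Assuming an alpha error level of 0.05 (two-sided) and a power of 0.8, a total sample size of n=60 will be sufficient to detect" a Cohen's d of 0.65, described as a medium effect. The synopsis repeats the sentence under the number of participants. Section 6.1 fixes the size: "A total of 60 patients will be included".

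The calculation names no test family and gives no number per condition. It states no correlation between baseline and follow-up, no correlation among repeated scores, no intracluster correlation and no dropout rate. Section 11.2 adds that the trial is a pilot for qualitative experience and preliminary efficacy, and that a large confirmatory trial will follow if the results are encouraging.

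Three other places bear on the calculation:

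- Section 6.1 makes two wards the clusters, each crossing over between conditions. On the sequence it says "The order (TAU plus SleepExpert first vs. TAU plus sleep monitoring first) will be randomly allocated in a 1:1 fashion".
- Section 11.4.2 plans a linear mixed model on the four follow-up ISI scores, with a baseline covariate and random patient and cluster effects.
- Section 9.2.5 replaces non-starters, but for those who have started it says "Patients who started the intervention but who were prematurely withdrawn from the study will not be replaced by newly enrolled patients".

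**The concern.** Cohen's d is the standardised difference between two means, so the natural reading of Section 11.2 is a two-sample comparison. On that reading, alpha, sidedness, power, effect and sample size are all stated, and they do not fit together: 60 is too few for a two-sided test.

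The primary objective (Section 4.2) is a significance test on the ISI, so the power claim affects how the result will be read. If the trial is non-significant, a reader who trusts Section 11.2 would take it as evidence against d=0.65 from a test with 80% power. The same figures could also be carried into the planning of the confirmatory trial.

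**Working it through.** **Inputs**

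- Alpha 0.05 two-sided, power 0.80, d=0.65, total N=60: Section 11.2 and the synopsis.
- 30 patients per condition: assumed. The protocol gives no split; two wards each provide both conditions, in opposite orders.
- Two-sample t-test: assumed, because the effect is given as Cohen's d.

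**Power at 30 per condition (noncentral t)**

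The noncentrality is δ = d·√(n/2) = 0.65 × √15 = 2.517, with 58 degrees of freedom.

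- Two-sided: the critical value is 2.002 and power is **69.7%**. The normal approximation gives Φ(2.517 − 1.960) = 71.1%.
- One-sided: the critical value is 1.672 and power is **80.04%**.

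**Sample size for 80% power**

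- Normal approximation, two-sided: n = 2(1.960 + 0.842)²/0.65² = 37.2, so 38 per condition (76 in total).
- Noncentral t, two-sided: the solution is 38.14. With 38 per condition power is 79.9%, and with 39 it is 80.9%, so **78 in total**.
- Noncentral t, one-sided: the solution is 29.97, so 30 per condition, **60 in total**.

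**Effect detectable with 80% power at N=60**

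- Two-sided: d = 0.736.
- One-sided: d = 0.6496, which rounds to the stated 0.65.

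The one-sided setting therefore reproduces the stated N, power and effect together. The two-sided setting does not.

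**Other routes to a two-sided 60**

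| Basis | Result |
|---|---|
| Mann-Whitney (relative efficiency 0.955) | 41 per condition, 82 in total |
| 60 per condition | 94% power |
| Single-endpoint ANCOVA, d/√(1 − r²) | N=60 needs a baseline correlation r of about 0.47 |
| Repeated-measures ANOVA, group effect, 4 measurements | N=50 at correlation 0.5; N=60 at 0.7 |
| Repeated-measures ANOVA, interaction (2, 4 or 5 measurements) | N=40 or fewer in every setting tried |

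The covariate and repeated-measures routes all depend on a correlation that the protocol does not state.

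**Sensitivity on the two-sample basis**

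- Attrition of 10% (27 per condition) gives 65.0% power, and 20% (24 per condition) gives 59.7%. The 78 patients would become 78/0.9 = 87 or 78/0.8 = 98. Both rates are assumed.
- Clustering: 60 patients over 2 wards × 2 periods is 15 per ward-period. With an assumed within-period ICC of 0.05 and between-period ICC of 0.025, the design effect is 1 + 14 × 0.05 − 15 × 0.025 = 1.325. Then δ = 2.517/√1.325 = 2.187, and power is about 58%.
- In the other direction, an assumed baseline correlation of 0.5 gives 81.6% before clustering and attrition. It falls to 72.1% with the 20% attrition, or 70.0% with that design effect.

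**The case against.** The strongest objection is that the 69.7% belongs to a test the protocol does not plan. Section 11.2 names no test, the objective is worded as a group-by-time interaction, and Section 11.4.2 uses four follow-up scores and the baseline. Take one common correlation ρ between all visits and a constant effect of 0.65 at each. The baseline-adjusted mean of four scores then has relative variance (1 + 3ρ)/4 − ρ², which is 0.375 at ρ=0.5. For ρ from 0.3 to 0.6, power at 60 patients is about 98% to 99%. With 20% attrition it is 94% to 97%, and with the design effect of 1.325 as a rough further multiplier it is 87% to 91%.

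This part stands: the planned analysis may well have more than 80% power, and the 58% and 60% figures must not be read as the power of the planned model. It does not rescue Section 11.2, which states no correlation, number of measurements or test from which 60 could be derived. The favourable figures also need the full effect at every visit, including weeks 1 and 2; power would be lower if the effect varies or if week 26 alone matters.

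Two further points are fair. No document mentions a one-sided test, so that explanation remains an inference from the match. And for a pilot the consequences are milder than for a confirmatory trial: nothing in the protocol says that this calculation will drive later planning. The missing allowances for clustering and attrition are design gaps, separate from the arithmetic error.

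**Conclusion.** The power statement is wrong as written. Read as a two-sample comparison of means with equal groups, 60 patients give 69.7% power for d=0.65 at two-sided 5%, about 10 percentage points below the claim. The stated power would need 78 patients, 18 more than planned, or an effect of d=0.74. A one-sided 5% test matches the stated figures almost exactly.

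This rests on two assumptions: the two-sample test, which the use of Cohen's d implies, and the 30/30 split. It is not a finding that the planned mixed model is underpowered; that cannot be settled without correlations, an ICC and an attrition rate, which the protocol does not give. On either reading the sentence needs correction. The trial's pilot purpose makes this a correction of reporting, not a reason to change the design.

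**What to change.** Keep 60 patients and replace the power sentence in Section 11.2 and in the synopsis with wording such as:

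> With 60 patients (30 per condition), a two-sided 5% two-sample comparison has about 70% power for d=0.65 and 80% power for d=0.74, before allowance for clustering and attrition.

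If the sponsor relies instead on the baseline-adjusted repeated-measures model, Section 11.2 should name that model and the effect tested. It should also state the assumed baseline and within-patient correlations, the ward-period ICCs and the attrition rate, and give the resulting power. If a one-sided test was intended, the text should say so and justify it.

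The first option costs two sentences and no additional patients, procedures or analyses. The price is a less favourable stated power. The model-based option takes a short calculation and a few stated assumptions.

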11.3 Statistical criteria of termination of trial

no statistical criteria for termination of trial have been formulated.

11.4 Planned Analyses

At the start of recruitment, a statistical analysis plan (SAP) will be written. The plan determines all necessary data preparation steps (e.g. additional validations, generation of new variables), definitions (e.g. analysis sets), and statistical analyses (e.g. models, outputs such as tables and graphs).

11.4.1 Datasets to be analysed, analysis populations

All analyses will be done on the as-treated analysis considering the cross-over design.

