5. STUDY OUTCOMES

5.1 Primary Outcome

The primary outcome will be insomnia severity measured with the Insomnia Severity Index (ISI) (Bastien et al., 2001). The ISI will be administered before the intervention (T0) and one, two, 12, and 26 weeks after the start of the intervention.

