6.2.3 Other methods of minimising bias

- The primary applicant is a staff member at the sleep clinic of the University Psychiatric Services Bern. The resources at this established, specialized sleep clinic will ensure that included patients are carefully diagnosed, i.e. that only patients fulfilling the defined eligibility criteria will be included. This ensures generalizability of the results to the intended population.
- Study attrition and reasons for dropout will be carefully documented throughout the study period.
- An intention to treat analysis will be provided since a per-protocol analysis may result in biased effects if many patients drop out due to (perceived) inefficacy.
- The outcome measures are widely used, valid, and reliable measures that have been recommended by experts for the research assessment of insomnia (Buysse, Ancoli-Israel, Edinger, Lichstein, & Morin, 2006).
- Therapists will be experienced, well-trained, and supervised.
- The trial will be registered in a publicly accessible database before recruitment of the first subject. Hypotheses and the analysis plan will be made publicly available. This precludes that the analysis plan is changed after inspection of the data ("fishing for significances").

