7.3 Assignment to study groups

The two clusters (UPD wards) will be assigned to one of the following two study sequences – while one cluster will follow the first sequence, the other one will follow the second sequence. Which ward will follow which study sequence will be randomly assigned.

- TAU plus SleepExpert first for 4 months; fade-out for one month; wash-out for one month; TAU plus sleep monitoring for 4 months
- TAU plus sleep monitoring for 4 months; fade-out for one month, wash-out for one month; TAU plus SleepExpert for 4 months

During the TAU plus SleepExpert and TAU plus sleep monitoring phases, patients will be actively recruited. During the fade-out phases, no active recruitment will take place, but already recruited patients will be able to complete their treatment. During the wash-out phase, no recruitment and no study-related treatment will take place.

Depending at which stage of the study the ward stands at the time point when a subject is admitted to the ward, her or she will either receive TAU plus SleepExpert or TAU plus sleep monitoring, or, if admitted during the wash-out phase, the subject will not be able to participate in the trial.

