11.4.5 Deviation(s) from the original statistical plan

The SAP is a version-controlled document which allows to track all changes to the statistical analysis. Any post-hoc changes will be transparently reported in all publications.

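### Section 11.4.1 puts every analysis on an undefined as-treated basis, section 6.2.3 promises intention to treat, and nothing says which is primary

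*Combined protocol and SAP*

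**What the plan says.** Section 11.4.1 reads in full: "All analyses will be done on the as-treated analysis considering the cross-over design". It does not say what counts as having been treated, or how to classify a patient who never uses SleepExpert or stops using it. Section 11.4.2 specifies the mixed model for the four follow-up ISI scores without naming a population, so 11.4.1 governs it.

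Section 6.2.3 says: "An intention to treat analysis will be provided since a per-protocol analysis may result in biased effects if many patients drop out". It does not call that analysis primary. It adds, of public registration and posting of the plan: "This precludes that the analysis plan is changed after inspection of the data".

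Section 11.4 leaves detail to a statistical analysis plan to be written at the start of recruitment: "The plan determines all necessary data preparation steps (e.g. additional validations, generation of new variables), definitions (e.g. analysis sets"). That plan is not part of the document. Section 11.4.5 adds: "The SAP is a version-controlled document which allows to track all changes to the statistical analysis".

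Condition is set by ward and calendar time. Section 7.3 assigns a patient "Depending at which stage of the study the ward stands at the time point when a subject is admitted to the ward". Sections 8.5 and 9.2.5 keep patients who stop the intervention, but do not withdraw, in follow-up. Sections 9.2.5 and 11.5 replace patients who drop out before treatment starts.

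**The concern.** The two instructions cannot both be followed as written. If all analyses are as-treated, there is no room for the promised intention-to-treat analysis. If that analysis is provided, not all analyses are as-treated. Two statisticians drafting the detailed plan, one from 11.4.1 and one from 6.2.3, could define different primary populations and both claim to follow the protocol.

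At stake is the comparison that randomisation supports. What is randomised is the order of conditions on each ward, so the protected contrast is between patients grouped by the ward phase in which they were recruited. Grouping by treatment taken gives that up, because uptake of a behavioural programme in patients with severe mental disorders may go with prognosis. Since patients who stop the intervention stay in follow-up, the data set will hold outcomes that the two approaches could classify differently.

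**Working it through.** No figure in the plan depends on the choice of population, so the core check is a reading of the text.

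**1. The passages side by side**

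| Question | 11.4.1 | 6.2.3 | Elsewhere |
|---|---|---|---|
| Basis | As-treated, all analyses | Intention to treat, to be provided | 11.4.2 names none |
| Definition | None | None | Left to a later plan (11.4) |
| Which is primary | Not stated | Not stated | Not stated |

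**2. Two readings of 11.4.1**

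- Ward-phase reading: treated means recruited while that condition ran on the ward (7.3). The labels equal the intention-to-treat labels, and the bias from this source is 0.
- Literal reading: treated means treatment taken. The labels can then differ from assignment.

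**3. Illustration of the literal reading (all rates assumed)**

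Assume no true effect, 30 patients per arm by ward phase, SD 1, a two-sided 0.05 test and no clustering. A share p of SleepExpert-phase patients take none of it and do d SD worse than the others. The control arm contains the same mix.

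- Left out: bias = p·d, SE = √(1/(30(1−p)) + 1/30).
- Counted as control: bias = 2pd/(1+p), SE = √(1/(30(1−p)) + 1/(30(1+p))).

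| p, d | Left out: bias (rejection rate) | Counted as control: bias (rejection rate) |
|---|---|---|
| 0.05, 0.25 | 0.0125 (5.0%) | 0.024 (5.1%) |
| 0.10, 0.50 | 0.050 (5.4%) | 0.091 (6.4%) |
| 0.20, 0.75 | 0.150 (8.5%) | 0.250 (15.8%) |

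If these patients do better instead, the sign reverses. If baseline ISI, a covariate in 11.4.2, carries half of the gap, the middle row falls to 0.025 and 0.045; if it carries all of it, to 0. The last column is the less plausible one, because nothing says that a SleepExpert-phase patient who takes nothing receives the monitoring app that defines control (8.1.2).

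**4. Readmission as a route to differing labels**

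Section 6.1 says: "After a washout-phase of two months, they will then be allocated to the other group for another 4 months". Hence the control-first ward recruits controls in months 0–4 and opens SleepExpert at month 6. Section 5.1 says: "The ISI will be administered before the intervention (T0) and one, two, 12, and 26 weeks after the start of the intervention". At 30.44 days per month, T2 (14 days) is 0.46 months, T3 (84 days) is 2.76 and T4 (182 days) is 5.98. Assume even recruitment over the 4 months.

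- T2 falls at month 4.46 at the latest, before month 6. The same holds for T1.
- T3 falls after month 6 only if recruitment was after month 6 − 2.76 = 3.24: (4 − 3.24)/4 = 19% of these patients.
- T4 falls after month 6 if recruitment was after month 6 − 5.98 = 0.02: about 99%.

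This concerns only first-phase control patients on the control-first ward, about 15 of 60 if recruitment is even across wards and phases, and mainly one of their four follow-up scores. A label changes only if such a patient is also readmitted and receives SleepExpert. The eligibility criteria in 7.1 do not bar an earlier participant, but no readmission rate is given.

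**The case against.** The strongest reply is that 11.4.1 qualifies as-treated by the cross-over design, and that in this trial condition follows the ward's phase, so as-treated may be the sponsor's term for analysis by ward phase. That is a fair reading, and under it nothing is biased. It stands as a possibility, but the text does not state it, and one sentence would settle it.

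Second, 6.2.3 contrasts intention to treat with per-protocol, not with as-treated, and does not call it primary. This is true. The conflict is with the word all in 11.4.1, and the promised analysis is left without a role.

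Third, analysis sets are to be defined in a plan that will be public and version-controlled. This limits choice after the data are seen. We cannot say that the set stays undefined, only that the protocol hands the author of that plan two incompatible instructions.

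Fourth, this is a pilot meant to give preliminary efficacy data (11.2), and the middle row of the illustration is small. That also stands, and the case does not rest on those figures.

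A reader might infer from the calendar overlap that nearly all first-phase controls cross over. Overlap in time is not exposure: readmission and receipt of SleepExpert are also needed, and neither can be quantified. A reader might also infer that replaced non-starters are dropped from the analysis. Sections 9.2.5 and 11.5 say that they are replaced, not that their data are removed.

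**Conclusion.** The point holds as a contradiction in the protocol: all analyses, the primary one included, are as-treated without a definition, an intention-to-treat analysis is also promised, and neither is named as primary. It should be settled before outcomes are analysed by condition.

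The documents do not support the stronger claim that the primary result will be biased, or by how much. The bias from this source is 0 under the ward-phase reading. Under the literal reading it depends on uptake and on prognosis by uptake, which the documents do not give. The 0.01 to 0.25 SD in the illustration shows only what assumed rates would produce. Readmission is a possible, unquantified further route, confined to first-phase controls on the control-first ward and mainly to T4.

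**What to change.** Replace 11.4.1 with: *The primary analysis is by intention to treat: every enrolled patient is analysed in the condition assigned to the ward phase in which the patient was first recruited, whatever treatment was taken.* Define as-treated and keep it only as a labelled sensitivity analysis. State that any non-starter replaced under 9.2.5 and 11.5 is counted and reported by arm, and that data already collected from such patients stay in the intention-to-treat set. Carry the same wording into the statistical analysis plan.

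The cost is protocol and analysis-plan wording and a count by arm. Patients who discontinue the intervention are already followed up (8.5, 9.2.5). Non-starters are treated separately there, so following them up, or changing the imputation trigger in 11.5, would be a further change and is not part of this fix. A non-starter with only T0 has no follow-up score and adds no outcome to the model in 11.4.2.

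The statistical downside is dilution. If a share q of the SleepExpert arm gains nothing, the planned 0.65 becomes 0.65(1−q). For assumed q of 5%, 10% and 20% this is 0.62, 0.585 and 0.52. With 30 per arm (two-sided t test, unadjusted, no clustering), power falls from 70% to 65%, 61% and 51%. The 70% is our figure; section 11.2 states 80% for 60 patients, which the two-sided t test does not reproduce. That is a separate matter.
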